4.1.5 Statistical modelling

In general, continuous variables will be analyzed using a MMRM if multiple post-baseline measurements are collected. If only an endpoint measurement is collected, analysis of covariance (ANCOVA) will be used. The MMRM/ANCOVA analysis will be treated as the primary analysis method for continuous efficacy endpoints. The statistical analysis of categorical variables will be done using a stratified Cochran-Mantel-Haenszel (CMH) test.

Standard diagnostic approaches will be used to verify that the key statistical assumptions of the MMRM/ANCOVA and CMH test hold.

If the distributional assumptions of the MMRM for the primary analysis do not hold, alternative models will be explored using appropriate transformed data.

4.2 Analysis methods

4.2.1 Study disposition and baseline demographics

Unless otherwise stated, for patient disposition and baseline demographics outputs, percentages will be calculated out of the total number of patients in the analysis set displayed in the output, overall and by treatment group (i.e., each denominator will also include the number of patients with missing/unknown values for the endpoint).

4.2.1.1 Patient disposition

Patient disposition information for all patients who provided informed consent, including counts and percentages of patients who entered placebo lead-in, were randomized, received randomized treatment, completed the treatment period, entered the safety follow-up period and completed the safety follow-up period, will be summarized. Patients who were not randomized (including reasons for non-randomization), patients who did not receive randomized treatment, patients who discontinued the randomized treatment period early (including reasons for early discontinuation), patients who did not enter the safety follow-up period (including reasons for not entering) and patients who discontinued the safety follow-up period early (including reasons for early discontinuation), will be summarized overall and for each treatment group.

No percentage will be displayed for number of patients who provided informed consent. The denominator for percentages for the patients entered placebo lead-in will be the number of patients who provided informed consent. The denominator for other percentages will be the total number of patients in the ITT analysis set, overall and by treatment group. A listing of patient

disposition will be provided, including reasons for early discontinuation and reasons for not entering safety follow-up.

The number and percentage of patients in each analysis set will also be reported overall and by treatment group. The denominator for percentages will be the total number of patients in the ITT analysis set, overall and by treatment group.

4.2.1.2 Demographics and baseline characteristics

Demographic and baseline characteristics will be summarized for the ITT, FAS, evaluable, safety and SFU analysis sets overall and by treatment as per below table.

Table 2 Demographics and baseline characteristics

Demographic and baseline characteristics	Categories
Age years (continuous)	
Age group 1 (years) (categorical)	<10 10 to 17 >17
Age group 2 (years) (categorical)	<10 10 to 12 13 to 16 > 16
Sex	Male Female
Race	White Black or African American Asian Native Hawaiian or Other Pacific Islander American Indian or Alaska Native Hispanic Other

Demographic and baseline characteristics	Categories
Region	Africa Asia Europe Latin America USA
Country	Brazil India Mexico Republic of Korea Russia South Africa USA
Height (cm), (continuous)	
Weight (kg), (continuous)	
Body Mass Index (BMI) (kg/m ²), (continuous)	
Height population percentile group (categorical)	<3 3 to <85 85 to <97 ≥97
Weight population percentile group (categorical)	<3 3 to <85 85 to <97 ≥97
BMI population percentile group (categorical)	<3

Demographic and baseline characteristics	Categories
	3 to <85
	85 to <97
	≥97
Waist Circumference (cm), (continuous)	
Hip Circumference (cm), (continuous)	
Baseline HbA1c %, (continuous)	
HbA1c stratum	≤8.0%
	>8.0%
Background Diabetes therapy	Naïve
	Metformin
	SU
	Metformin + SU
Duration of Diabetes (years), (continuous)	
Duration of Diabetes (years), (categorical)	<1
	≥1 to ≤5
	>5
Baseline FPG (fasting serum glucose), mg/dL, (continuous)	
Baseline FPG (fasting serum glucose), mmol/L, (continuous)	
ECG	Abnormal
	Clinically significant
	Not clinically significant
	Normal
Baseline eGFR (mL/min/1.73 ²) (continuous) (Bedside Schwartz equation)	

Demographic and baseline characteristics	Categories
Baseline eGFR (mL/min/1.73 ²)	≥125
(Bedside Schwartz equation)	<125
Baseline eGFR (mL/min/1.73 ²) (continuous) (CKD-Epi equation)	
Baseline Tanner Stage (repeat for each of Pubic hair-female, breast-female, pubic hair- male, genitals-male, overall)	Stage 1
	Stage 2
	Stage 3
	Stage 4
	Stage 5

Patient's age (years) and ECG will be taken from the Case Report Form (CRF) at screening.

If a patient switches to a different site during the study, the patient will be summarized at the site he/she originally enrolled in, regardless of when the patient switched sites.

Region will be categorized as following:

Africa - South Africa

Europe - Russia

Asia - India, Republic of Korea

Latin America - Brazil, Mexico

USA - USA.

BMI will be calculated as the ratio of patient's weight (in kilograms) to the square of the patient's height (in meters): $BMI = \text{kg}/\text{m}^2$. The Investigator-calculated BMI will not be summarized or listed. Height is collected in cm and will be converted to meters before calculating BMI by dividing by 100.

Percentile of body weight, height and BMI percentile will be determined based on the standardized growth chart for boys and girls.

Values and percentiles will be listed for height, body weight and BMI.

Duration of diabetes (years) will be calculated using the screening visit date and the date of diabetes diagnosis (see below).

If date of diabetes diagnosis is...	Then duration of diabetes (years) is...
Complete date	(Date of screening – Date of diabetes diagnosis + 1) / 365.25
Partial date (a) Year and month are not missing, but day is missing (b) Year is not missing, but month and date are both missing (b1) Year of diabetes diagnosis is different from the year of screening (b2) Year of diabetes diagnosis is the same as year of screening	(a) Impute missing day 1 st of the month, then use complete date rule (b1) Difference between year of diabetes diagnosis and year of screening (b2) 2/12 (2 months)

4.2.1.3 Medical/surgical history

All medical/surgical history (pre-existing conditions) by each system organ class (SOC) and preferred term (PT) will be summarized by treatment group for the safety analysis set in accordance to the terminology of the latest version of the Medical Dictionary for Regulatory Activities (MedDRA) available at database lock (DBL).

Conditions will be defined as pre-existing if the start date is on or before the date of informed consent.

Percentages will be calculated out of the total number of patients in the analysis set displayed in the output, overall and by treatment group.

4.2.1.4 Prior and concomitant medications

All medications will be coded using the latest version of WHO Drug Dictionary (WHODD) available at DBL.

Medications will be classified as:

- Pre-treatment medication: Medications stopped prior to first dose of randomized study medication (or all medications recorded for patients who did not receive randomized study medication)
- Prior concomitant medication: Medications started prior to and that continue past the first dose of randomized study medication.
- New concomitant medication: Medications with a start date on or after the first dose of randomized study medication up to but not including Visit 11 (Week 28/ED)
- Post-treatment medications: Medications with a start date on or after last dose of study medication

A listing of all medications will be produced.

The number and percentage of patients receiving prior concomitant and new concomitant medications will be summarized by treatment and ATC classification (level 4) for the ITT analysis set. Prior concomitant and new concomitant medications will be combined for summary tables. This will be repeated for the safety follow-up analysis set.

Prior antidiabetic concomitant medications will be summarized separately by reported term for the ITT and safety follow-up analysis sets.

Rescue therapy will be summarized by ATC classification (level 4) and generic term for the ITT and safety follow-up analysis set.

A listing of rescue medications will be provided.

Pre-treatment medications and post-treatment medications will be summarized separately by treatment and ATC classification (level 4) for the ITT analysis set. Post-treatment prescription medications will also be summarized by actual treatment during the randomized period, ATC classification (level 4) and generic term for the safety follow-up analysis set.

Medications with start/stop dates that are partially/completely missing will be imputed as described in [Appendix 4](#).

Review of unique combinations of ATC code classifications and generic terms captured will be performed by a physician prior to database lock to confirm prohibited medication use including the following:

- alpha-glucosidase inhibitors, meglitinide or pramlintide
- inhaled steroids at a dose equal to or above 1000 µg Flovent® (fluticasone propionate) daily
- oral steroids
- thiazolidinedione

Prohibited medications will be listed.

4.2.2 Treatment compliance

No specific study data was collected for analysis of study medication treatment compliance.

4.2.3 Exposure

Exposure to study medication will be presented for the treatment period (Week 0 to Week 28) for the safety analysis set and for the safety follow-up analysis set.

Duration of exposure in days will be calculated as the date on the last dose CRF form (STR_LD) minus the date on the first dose CRF form (STR_FD) + 1.

Dose interruptions will not be taken into consideration for calculation of duration of exposure.

The mean, SD, median, minimum, and maximum duration of exposure will be provided by treatment group. Duration of exposure will also be categorized into fixed intervals as follows, with number of patients and percentage summarized by treatment group:

- 1-13, 14-27, 28-55, 56-83, 84-111, 112-139, 140-167, 168-195, ≥196 days

In addition, duration of exposure will also be summarized by country and treatment group.

4.2.4 Efficacy analysis

4.2.4.1 Estimands

Estimands for the study are defined in Table 3. Intercurrent events (IE) that may occur during the study are receipt of rescue therapy, IP discontinuation and study withdrawal.

Table 3 Estimand framework

Estimand	Attributes			
	Population	Variable	Intercurrent event (IE) strategy	Population-level summary
Primary	Evaluable	Change in HbA1c from baseline to Week 28	All IEs: Data after event excluded. Hypothetical approach due to missing at random (MAR) assumption of MMRM analysis.	Least squares mean difference in CFBL at Week 28 between Total EBID and PBO
Sensitivity to primary	Evaluable	Change in HbA1c from baseline to Week 28	All IEs: Data after event excluded. Hypothetical approach using multiple imputation (MI) pattern mixture modelling.	Least squares mean difference in CFBL at Week 28 between Total EBID and PBO
Supplementary to primary	Evaluable	Change in HbA1c from baseline to Week 28	Rescue and IP discontinuation: Data after event included. Treatment policy approach Withdrawal from study prior to Week 28: Hypothetical approach due to MAR assumption of MMRM analysis	Least squares mean difference in CFBL at Week 28 between Total EBID and PBO

	Attributes			
Estimand	Population	Variable	Intercurrent event (IE) strategy	Population-level summary
Sensitivity to supplementary of primary	Evaluable	Change in HbA1c from baseline to Week 28	Rescue and IP discontinuation: Data after event included. Treatment policy approach Withdrawal from study prior to Week 28: Hypothetical approach using MI pattern mixture modelling	Least squares mean difference in CFBL at Week 28 between Total EBID and PBO
Secondary 1	Evaluable	Proportions of patients having HbA1c goals of <7%, ≤6.5%, and <6.5% at Week 28	All IEs: Data after event excluded. Composite approach used, with patients with missing data at endpoint treated as non-responders	Difference in proportion of responders at Week 28 between Total EBID and PBO
Sensitivity to secondary 1	Evaluable	Proportions of patients having HbA1c goals of <7%, ≤6.5%, and <6.5% at Week 28	All IEs: Data after event excluded. Hypothetical approach using MI pattern mixture modelling	Difference in proportion of responders at Week 28 between Total EBID and PBO
Secondary 2	Evaluable	Change in HbA1c from baseline to Week 28 and each intermediate visit	All IEs: Data after event excluded. Hypothetical approach due to missing at random (MAR) assumption of MMRM analysis	Least squares mean difference in CFBL at Week 28 and each intermediate visit between Total EBID and PBO

	Attributes			
Estimand	Population	Variable	Intercurrent event (IE) strategy	Population-level summary
Sensitivity to secondary 2	Evaluable	Change in HbA1c from baseline to Week 28 and each intermediate visit	All IEs: Data after event excluded. Hypothetical approach using multiple imputation (MI) pattern mixture modelling	Least squares mean difference in CFBL at Week 28 and each intermediate visit between Total EBID and PBO
Continuous secondary and exploratory efficacy endpoints measured post-baseline at a single endpoint	Full analysis set	Change in XX* from baseline to Week 28	All IEs: Data after event excluded. Hypothetical approach due to missing at random (MAR) using MI ANCOVA analysis	Least squares mean difference in CFBL at Week 28 between Total EBID and PBO
Other continuous secondary and exploratory efficacy endpoints	Full analysis set	Change in HbA1c from baseline to Week 28 and each intermediate visit	All IEs: Data after event excluded. Hypothetical approach due to missing at random (MAR) assumption of MMRM analysis.	Least squares mean difference in CFBL at Week 28 and each intermediate visit between Total EBID and PBO
Exploratory	Safety	Change in eGFR from baseline to Week 28 by baseline eGFR category	All IEs: Data after event excluded. Hypothetical approach due to MAR assumption of MMRM analysis.	Least squares mean difference in CFBL at Week 28 between Total EBID and PBO
Sensitivity to exploratory	Safety	Change in eGFR from baseline to Week 28 by baseline eGFR category	Rescue and IP discontinuation: Data after event included. Treatment policy approach.	Least squares mean difference in CFBL at Week 28 between Total EBID and PBO

	Attributes			
Estimand	Population	Variable	Intercurrent event (IE) strategy	Population-level summary
			Withdrawal from study prior to Week 28: Hypothetical approach due to MAR assumption of MMRM analysis.	

*where XX are FSG, FSI, SMBG, HOMA-B, HOMA-S, hip and waist circumference.

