### **6.1.6. Early Discontinuation Visit**

If a patient discontinues after randomization but prior to completion of the study treatment period, the patient will be asked to return as soon as possible to the study site for an early discontinuation visit. The early discontinuation visit procedures are described in detail in the Study Schedule ([Attachment 1](#)). The patients will not receive exenatide or placebo; however, a treatment regimen, as deemed clinically appropriate, should be initiated. Investigative staff should complete a study summary page for each patient. Patients who discontinue after randomization but prior to completion of the study treatment period should continue with the safety follow-up addendum unless the patient is lost to follow-up or withdraws consent. Patients who do not have height assessments at study-site visits over a 6-month interval prior to discontinuation of study medication will enter the safety follow-up period (Protocol Addendum 4).

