Patients who discontinue the study drug and/or study early will have early discontinuation procedures performed as shown in the Study Schedule ([Attachment 1](#)) and be placed on appropriate active antidiabetes therapy. Patients who discontinue study drug administration prior to Visit 11 will enter the safety follow-up period. Refer to the safety follow-up addendum for guidance.

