### 4.2. Summary of Study Design

Following discontinuation of study drug administration, patients with a height difference of at least 5 mm between Visit 3 and Visit 11 will enter the safety follow-up period. Patients who discontinue study drug administration prior to Visit 11 will also enter the safety follow-up period. During this period, patients will return to the study site at approximately 6-month intervals for a period of up to 3 years or until the difference between 2 height measurements over a 6-month interval is less than 5 mm (whichever comes first). Patients who do not have height assessments at study-site visits over a 6-month interval prior to discontinuation of study medication will enter the safety follow-up period. Patients will not receive any study drug but may be treated with a diabetes treatment regimen deemed appropriate by the investigator or healthcare provider. During the safety follow-up period, the following will occur: AESIs and ongoing prescription medications will be reviewed; height, weight, and Tanner pubertal stage will be assessed; and CEA and calcitonin concentrations will be measured. Refer to the Study Schedule ([Attachment 1](#)) for more information.

Patients who have achieved the final height requirement of a change of less than 5 mm between Visit 3 and Visit 11 of the treatment period will be excluded from the safety follow-up period.

Patients who completed the protocol prior to this addendum will be evaluated for inclusion in the safety follow-up period where possible ([Section 4.2.1.1](#)).

The entire study design including the safety extension period is illustrated in [Figure GWBQ\(4\) 1](#).

Abbreviations: BID = twice a day

a Metformin (Met) or sulfonylurea (SU) or combination of Met and SU, with or without diet and exercise, or naïve to antidiabetic agents defined as being treated with diet and exercise alone.

b The volume of placebo is equivalent to 5 µg or 10 µg exenatide.

c Scheduled telephone visit.

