Due to the availability of other more conveniently administered therapies e.g. oral, once daily (QD), or once weekly (QW), recruitment to this study has been slow/difficult despite extensive efforts by the sponsor. The planned number of patients will take unreasonably long to recruit so a decision was made with agreement by the European Medicines Agency and Food and Drug Administration to stop recruitment and to pool patients from both exenatide arms and compare the pooled arm with placebo. With a total of 122 patients randomized (Total EBID:Placebo 2:1), the study should have approximately 87% power to detect a difference between Total EBID and placebo assuming the true mean changes in HbA1c are -0.7, -0.5, and 0 for patients receiving exenatide 10 µg BID, exenatide 5 µg BID, and placebo BID, respectively. The combined effect of the Total EBID doses compared to placebo (mean difference) is assumed to be -0.6 with a common standard deviation of 1% at the 5% significance level without consideration of patient discontinuation and impact on effect size. An assumed effect size of -0.455 was considered in power calculation.

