4.2.4.2 Analysis of primary variable

The MMRM analysis of the primary endpoint in the Evaluable analysis set will be considered the primary analysis.

The primary efficacy analysis will compare treatment groups (Total EBID vs. PBO) with respect to change in HbA1c from baseline Visit 3 (Week 0) to Visit 11 (Week 28) using the MMRM approach. The model will include change in HbA1c as the dependent variable and treatment, baseline HbA1c, background diabetes therapy strata (drug naïve, metformin only, SU only, and metformin + SU), week of visit, baseline HbA1c-by-week interaction and treatment-by-week interaction as the fixed effects. The variance - covariance structure to be used for this modelling will be unstructured (UN); if the model does not converge with unstructured variance – covariance matrix, then autoregressive order 1 (AR [1]) and heterogeneous autoregressive order 1 (ARH [1]) structures will be tried and the covariance structure will be decided based on model convergence status and the Akaike information criterion. The restricted maximum likelihood (REML) method will be used for parameter estimation. The least squares (LS) mean, 2-sided 95% confidence interval, and p-value of the difference in the change of HbA1c between the Total EBID and PBO groups at Visit 11 (Week 28) will be provided. The mean (SD) observed HbA1c at baseline and Week 28 will also be given by treatment group.

HbA1c data from post-baseline visits (including ED) will potentially be included in the MMRM analysis. In addition, if a patient’s last available measurement during the 28-week assessment period is from an unscheduled visit or ED visit, the value will be programmatically mapped to the next closest scheduled visit and potentially included in the MMRM analysis. See Section 4.1.3 for details on missing data handling and Section 4.2.4.1 for details on handling of data after IEs.

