For patients who initiate rescue medication or discontinue IP and continue study participation, only data before initiation of rescue medication or up to and including date of discontinuation from IP will be included in the MMRM/ANCOVA analysis. If there is evidence that a measurement was taken prior to initiation of rescue medication, then this data will be included. If the measurement was taken on the date of initiation of rescue medication but time information is not available, then the measurement will be included. Data collected after discontinuation of IP will be excluded from analyses for all secondary efficacy endpoints.

Summaries and analysis of the primary endpoint will be performed in the Evaluable analysis set.

Assessment of homogeneity of treatment effect:

The homogeneity of treatment effect will be assessed by adding treatment by baseline interaction and treatment by strata interaction to the primary MMRM model as described in [Section 4.2.4.2](#). The same covariance structure as used for the primary analysis will be used for this model. The p-value for the interaction effects will be explored to identify the potential trend for non-homogeneity.

Descriptive summary of primary efficacy variable by visit

Actual, change and percent change from baseline values of HbA1c will be summarized using descriptive statistics by visit and treatment group. Plots of mean \pm standard error of mean for the change from baseline in HbA1c by visit and treatment group will be provided. Only OC summaries will be provided.

Subgroup analysis

The primary endpoint, change from baseline in HbA1c at week 28, will be summarized descriptively for subgroups of interest listed below. No statistical analyses will be conducted.

- Sex
- Age group: two different definitions.
 - Age (years) <10, 10 to 12, 13 to 16, >16
 - Age (years) <10, 10 to 17, and >17
- Race

Actual, change and percent change from baseline values of HbA1c will be summarized using descriptive statistics by visit and treatment group for each subgroup of the Evaluable analysis set. OC summaries will be provided.

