Step 3: The imputed data from Step 1 and Step 2, along with observed data will be analyzed using an MMRM model for the outcome of change from baseline with treatment, baseline HbA1c, background diabetes therapy strata (drug naïve, metformin only, SU only, and metformin +SU), week of visit, baseline HbA1c-by-week interaction and treatment-by-week interaction as the fixed effects. The variance - covariance structure to be used for this modelling will be unstructured (UN). The estimates from multiple imputed datasets will be combined using Rubin's combination rules for statistical inference (Rubin, 1987) using PROC MI ANALYZE.

The seed used will be 88281 for both steps 1 and 2.

At Step 1, if a categorical covariate has more than 2 levels, then dummy coding has to be performed to present it as either 0/1 or 1/2. If categorical variable has X categories ($X > 2$) then we would create $X-1$ dummy variables, using the rule described in the table below.

Table 4 Dummy variables

Category	Dummy variable 1	Dummy variable 2	...	Dummy variable X-1
A	1	0		0
B	0	1		0
...	0	0		0
X-1	0	0		1
X	0	0		0

A supplemental to the primary analysis and a sensitivity to the supplemental of the primary analysis will also be performed. In these analyses, data after rescue medication use or date of IP discontinuation will be included in the MMRM analysis and MI pattern mixture modelling.

Further sensitivity analysis will be as described in section 4.2.4.2, where it will compare active treatment group doses vs Placebo (EBID vs. PBO).

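### No HbA1c is scheduled after the early discontinuation visit, so the supplementary row's treatment-policy strategy for stopping study drug is largely unobserved at Week 28 and rests on the primary's MAR assumption

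*SAP*

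**What the plan says.** **What is promised.** SAP 4.2.4.1 names three intercurrent events: rescue, stopping study drug (IP discontinuation) and withdrawal from the study. The primary row of Table 3 drops data after any of them and calls the MAR-based MMRM a hypothetical strategy. The row supplementary to the primary reads "Rescue and IP discontinuation: Data after event included. Treatment policy approach", and leaves study withdrawal before Week 28 to MAR. SAP 4.2.4.3 confirms that "data after rescue medication use or date of IP discontinuation will be included in the MMRM analysis and MI pattern mixture modelling". The next row of the table keeps the same data and handles withdrawal by pattern-mixture multiple imputation (MI).

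**What is measured after drug is stopped.** Under Protocol 6.1.6, "the patient will be asked to return as soon as possible to the study site for an early discontinuation visit". Protocol 7.4 adds: "Patients who discontinue study drug administration prior to Visit 11 will enter the safety follow-up period", and has these patients start other antidiabetes therapy. In that follow-up (Protocol Addendum 4, section 4.2), "CEA and calcitonin concentrations will be measured", along with height, weight, Tanner stage, selected adverse events and prescription medication. HbA1c is not in the Addendum 4 schedule, and the note under SAP Table 9 confirms that the only laboratory tests are CEA and calcitonin.

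**Where the windows close.** SAP 3.6.6 ends the treatment period at the ED visit for early discontinuers. The Week 28 HbA1c window in SAP 4.3.1 runs from day 169 to the last day of that period.

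**The ED value.** Protocol Attachment 1 schedules HbA1c at ED. SAP 4.2.4.2 says "HbA1c data from post-baseline visits (including ED) will potentially be included in the MMRM analysis" and maps a last value from ED forward to the next closest scheduled visit. The same section says that, for patients who start rescue or stop drug but stay in the study, "only data before initiation of rescue medication or up to and including date of discontinuation from IP will be included in the MMRM/ANCOVA analysis".

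**The concern.** A treatment-policy strategy asks what HbA1c is at Week 28 whether or not the patient is still on drug. That needs outcomes measured off drug at or near Week 28. Here the row includes whatever was collected after the event, but for drug discontinuation the schedule collects almost nothing after the ED visit. The missing Week 28 values then go to the MMRM under MAR, the approach that the primary row labels hypothetical.

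What is at stake is interpretation. SAP 4.2.4.3 presents these analyses as a way to see the influence of drop-out and rescue. If the primary and supplementary estimates agree, a reader of the study report will probably conclude that the result withstands drug discontinuation. For that event the comparison is mostly between one assumption and itself.

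**Working it through.** **1. The plan's own figure.** SAP 1.3 gives about 87% power for 122 patients randomized 2:1, difference -0.6, SD 1%, two-sided 5%, ignoring discontinuation.
- SE = sqrt(1/81.33 + 1/40.67) = 0.192.
- Power = Φ(0.6/0.192 - 1.96) = 87.8%. A noncentral t calculation with 81 and 41 patients gives 87.4%. The figure reproduces.
- I therefore use -0.60 as the on-treatment effect.

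**2. Which HbA1c values can separate the two analyses at Week 28.**

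| Source | Primary | Supplementary |
|---|---|---|
| After rescue, still on study drug | excluded | included |
| ED visit, after last dose | unclear (see step 5) | included |
| After the ED visit | none scheduled | none scheduled |
| Discontinuer with no Week 28 value | MAR | MAR |

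**3. How many discontinuers have an ED value standing in for Week 28.** The documents do not say, so this rests on two assumptions: the 23% in SAP 1.3 (given there for the exenatide arms) applies to all arms, and stopping times are uniform over 28 weeks.
- Early discontinuers: 122 × 0.23 = 28.
- ED inside the day 169+ window: 28 × 28/196 = 4.
- Any ED after Week 20, mapped forward: 28 × 8/28 = 8.
- Without any Week 28 value: 28 - 8 = 20 to 28 - 4 = 24.

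For 10% to 30% discontinuation, about 2 to 10 patients have such an ED value.

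**4. What the label could hide.** Let d be the share stopping drug and L the share of benefit that they lose by Week 28. The treatment-policy effect is -0.60 × (1 - dL). If MAR returns about -0.60, it is too large by 1/(1 - dL) - 1. The values of L are assumptions. The formula leaves out any effect of therapy started after stopping.

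| d | L | Effect | MAR too large by |
|---|---|---|---|
| 23% | 0 | -0.60 | 0% |
| 23% | 0.5 | -0.531 | 13% |
| 23% | 1 | -0.462 | 30% |
| 10% | 1 | -0.54 | 11% |
| 30% | 1 | -0.42 | 43% |

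**5. The ED value in the primary.** One statement in SAP 4.2.4.2 admits ED HbA1c to the MMRM. The other cuts data at the date of drug discontinuation, but is worded for patients who remain in the study, a group for whom the protocol schedules no further treatment-period visits. SAP 4.2.5.1 recognises that the last dose can precede the ED visit. If the first statement governs, the two analyses differ only through post-rescue values. If the second governs, they differ through ED values as well.

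**The case against.** **Two strong readings are tempting, and neither is supported.** A reader might infer that no HbA1c at all exists after drug is stopped. In fact HbA1c is scheduled at ED, which may follow the last dose. A reader might also infer that the row simply duplicates the primary. It does not. It also covers rescue, and SAP 4.1.4 accepts that patients can take rescue while on study drug. Their later HbA1c enters this row and not the primary. How many such values exist is not in the documents. Both corrections stand. However, an ED value taken soon after stopping and mapped forward is not an off-drug Week 28 outcome, and post-rescue data from patients still on drug say nothing about those who stopped.

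**The same cell discloses MAR for study withdrawal.** This is true, and a patient who leaves at ED could be counted there. But the SAP lists drug discontinuation and withdrawal as separate events. If these patients count as discontinuers, the promised data are mostly absent. If they count as withdrawals, the treatment-policy clause covers almost nobody. The label misleads either way.

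**The next row already plans placebo-based MI.** This is the best point on the other side, because that row does stress the MAR assumption. But Table 3 ties the MI to withdrawal and calls it hypothetical. As SAP 4.2.4.3 describes it, a dropout keeps the mean reached at the last visit and then moves with placebo, so benefit already gained is retained. It is a useful sensitivity analysis, but it does not make the MMRM row a treatment-policy estimate.

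**Jump-to-reference is no more observed than MAR.** This stands. Discontinuers in both arms start other therapy, which most placebo patients do not receive. Any reference-based method must be presented as an assumption.

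**Conclusion.** The point holds in limited form. For drug discontinuation, the treatment-policy strategy in the supplementary row is largely unobserved at Week 28. Apart from ED values after the last dose and post-rescue values, the row uses the same MAR assumption as the primary. Agreement between the two should not be reported as robustness to drug discontinuation.

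The size is conditional. With 23% discontinuation and an on-treatment effect of -0.60, a MAR estimate near -0.60 would exceed the treatment-policy effect by 0% with no loss of benefit, about 13% with half lost and 30% with all lost. The documents do not support quoting 30% as the expected error, because they give no information on how much benefit discontinuers lose.

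Nor should the full-loss value of -0.46 be linked to the statement in SAP 1.3: "An assumed effect size of -0.455 was considered in power calculation". The closeness is suggestive, but the SAP neither derives -0.455 nor ties it to this estimand. The stated 87% power matches -0.6, whereas -0.455 gives about 66% with 122 patients.

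The primary estimand, its test and the sample size are not affected. A named estimand is mislabelled, and that should be corrected.

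**What to change.** - In SAP Table 3 and 4.2.4.3, relabel the MMRM row: post-rescue data included (treatment policy for rescue); hypothetical (MAR) for IP discontinuation without later HbA1c.
- For any row still called treatment policy for IP discontinuation, state that discontinuers' missing Week 28 values are imputed by reference-based MI adapted from the code planned in SAP 4.2.4.3, for example jump-to-reference. State openly that this is an assumption, because discontinuers start other therapy.
- In SAP 4.2.4.2, reconcile the statement admitting ED HbA1c with the cut-off at drug discontinuation, so that it is clear whether an ED value taken after the last dose enters the primary analysis.

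Cost: SAP wording, a modest extension of MI code already planned, and probably a smaller supplementary estimate. Apart from settling how ED values are handled, the primary analysis is unchanged.
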